#### 4.2.2.2 Restrictions on diet and life style

- Medication washout restrictions should be adhered to as described in table 4.2.2.1.
- Patients must remain in the building where the exercise and lung function testing is performed and must return to the laboratory at least 10 minutes prior to the start of each test.

Boehringer Ingelheim 15 APR 2016 BI Trial No.: 1237.28

c03207491-01 Trial Protocol Page 48 of 137

Proprietary confidential information © 2016 Boehringer Ingelheim International GmbH or one or more of its affiliated companies

- On PFT and exercise testing days (including the screening visit), patients must refrain from strenuous activity for at least 2-3 days prior to pulmonary function and exercise testing and throughout the testing period. Patients should also avoid cold temperatures, environmental smoke, dust or areas with strong odours (e.g. perfumes).
- Smoking should be discouraged for the 12 hours prior to lung function testing and throughout the study day and will not be permitted in the 30-minute period prior to lung function and exercise testing. If a patient has smoked in the 30-minute period prior to lung function and exercise testing, the visit should be rescheduled.
- Coffee, tea, chocolate, cola and other caffeine-containing beverages and foods, and ice-cold beverages are not allowed the morning of and during the lung function and exercise testing period. Decaffeinated beverages are acceptable.

## 4.2.2.3 Restrictions regarding women of childbearing potential

Women of childbearing potential must use the contraception methods described in the patient information.

#### 4.3 TREATMENT COMPLIANCE

On visit days, compliance will be guaranteed by administration of the trial drug under supervision of the investigator or designee. Each patient will be trained in the correct use of the Respimat® Inhaler using the training Respimat® Inhaler with inserted placebo cartridge on visit 1.

Compliance will be measured using the counter on the Respimat® device. Patients are requested to bring all used and unused trial medication with them when attending visits. The investigator or designee will review these records with the patient at all visits to assess treatment compliance in treatment phase. However, randomised patients will not be discontinued for lack of compliance without prior discussion with the (CML).

If the number of doses taken is not between 80-120%, site staff will explain the patient the importance of treatment compliance.

BI Trial No.: 1237.28

c03207491-01 Trial Protocol Page 49 of 137

Proprietary confidential information © 2016 Boehringer Ingelheim International GmbH or one or more of its affiliated companies

## 5. VARIABLES AND THEIR ASSESSMENT

#### 5.1 TRIAL ENDPOINTS

#### 5.1.1 Primary Endpoint

The primary endpoint is the change from baseline in intensity of breathlessness measured using the MBS-S at the end of the 3min Constant Speed Shuttle Test (CSST) after 6 weeks of treatment.

Change from baseline is defined as change from patient baseline. See Section 7.3.1.

#### 5.1.2 Secondary Endpoints

The following secondary endpoints will also be evaluated:

- Change from baseline in Inspiratory Capacity (IC) measured prior to exercise, after 6 weeks of treatment.
- Change from baseline in IC measured at the end of exercise, after 6 weeks of treatment
- Change from baseline in 1 hour post-dose FEV1, after 6 weeks of treatment.
- Change from baseline in 1 hour post-dose FVC, after 6 weeks of treatment.
- Change from baseline in intensity of Breathlessness (MBS-S) at 1min, 2min, and 2.5min during the 3min CSST after 6 weeks of treatment.
- Change in Chronic Respiratory Questionnaire Self Administered Individualized (CRQ-SAI) dyspnea domain score after 6 weeks of treatment.
- Change in Chronic Respiratory Questionnaire Self Administered Standardized (CRQ-SAS) dyspnea domain score after 6 weeks of treatment.

None of the primary or secondary endpoints are safety issues.

Boehringer Ingelheim BI Trial No.: 1237.28

c03207491-01 Trial Protocol

Page 50 of 137

Proprietary confidential information © 2016 Boehringer Ingelheim International GmbH or one or more of its affiliated companies

[figure not shown]
#### 5.2 ASSESSMENT OF EFFICACY

## **Constant Speed Shuttle Test**

At all sites, an ISWT will be performed at visit 1 for each patient. The test will be conducted according to the methodology described by Singh et al [R04-4259] with IC and physiological parameters measured using the mobile cardiopulmonary exercise equipment. At visit 2, starting at 4 km/h, the patient will complete up to three x 3min CSST at different sets of speeds (2.5, 3.25, 4, 5 or 6 km/h) to determine the highest speed that meet the following parameters:

- The patient can complete the entire three minutes of the test, and
- The patient achieves a BORG breathlessness rating of  $\geq 4$ .

The test will be conducted according to the methodology developed by Maltais et al, [P12-12739]. This speed selected at visit 2 will be used for all subsequent tests. At visit 3, a training 3min CSST will be performed using the speed selected at visit 2. At visits 4 and 7, a period baseline 3min CSST will be completed prior to dosing. At visits 5, 6, 8 and 9 a constant speed test will be conducted 2 hours (+15 minutes) after inhalation of the study medication.

The 3min CSST test methodology and speed selection is described in detail in Appendix 10.4 and manual of procedures.

BI Trial No.: 1237.28

c03207491-01 Trial Protocol Page 51 of 137

Proprietary confidential information © 2016 Boehringer Ingelheim International GmbH or one or more of its affiliated companies

## Modified BORG Scale

Before, during and at end-exercise, patients will be asked to estimate the intensity of breathing discomfort that they are experiencing by matching their subjective estimate to descriptive phrases that best describe the intensity of each sensation using the MBS-S. Details of the MBS-S are provided in Appendix 10.5.

## **Pulmonary Function Testing**

Spirometers and their use, including daily calibration, must meet ATS/ERS criteria [P05-12782]. Spirometry will be conducted using the site's own equipment. Patient will be in a seated position and it is preferable that the same trained individual performs the PFT for a given patient. The best of three efforts will be defined as the highest  $FEV_1$  and the highest FVC each obtained on any of three manoeuvres meeting the ATS criteria (to a maximum of five attempts). The highest  $FEV_1$  and FVC will be selected regardless of whether they come from different spirometric manoeuvres or from the same manoeuvre.

Predicted normal FEV1 values will be calculated for patients using the ECSC equations ( $\underline{R94}$ - $\underline{1408}$ , see  $\underline{Appendix 10.3}$ ).

If a patient is unable to complete the PFTs during a visit, the CML should be notified as soon as possible. The eCRF will be completed indicating the reason for stopping testing, rescue medication given (if any) and time of rescue medication. Patients who are unable to complete the study visit may leave the clinic only upon instruction from the supervising physician.

Reversibility testing [P05-12782] will be performed for the qualifying PFT at the Screening visit (visit 1): the procedure is described in Appendix 10.3. The post-bronchodilator measurements must meet the inclusion criteria specified in section 3.3.2.

#### **Inspiratory Capacity Measurements**

IC measurements will be performed during exercise testing as follows:

- ISWT at rest, during exercise and at the end of exercise
- 3min CSSTs at rest and at the end of exercise

IC measurements will be taken using mobile cardiopulmonary exercise equipment capable of measuring IC during the shuttle tests.

For IC taken at rest prior to exercise, at least three reproducible measurements should be obtained with a maximum of 5 measurements to be performed. The resting IC should be recorded as the mean of the two highest acceptable efforts.

For additional details on the IC maneuvers, please refer to Appendix 10.7 and manual of procedures.

BI Trial No.: 1237.28

c03207491-01 Trial Protocol Page 52 of 137

Proprietary confidential information © 2016 Boehringer Ingelheim International GmbH or one or more of its affiliated companies

## **Body Plethysmography**

Constant-volume variable-pressure body plethysmography will be used in the trial at visit 1 to assess eligibility and parameters to be measured will be FRC, IC and total lung capacity (TLC).

Measurements should be done in triplicate. The mean FRC value from the three manoeuvres will be recorded. The largest IC will be recorded. TLC will be calculated as mean FRC + largest IC. Body plethysmography should be done before spirometry.

#### **CRQ** Questionnaires

The CRQ questionnaires should be administered at the visits outlined in the FC and completed by the patients. They should be completed first during a study visit, prior to dosing and all study procedures. The CRQ-SAI should be completed prior to the CRQ-SAS. Please see Section 6.2 for the detailed order of administration of questionnaires at each visit.

The CRQ-SAS is a questionnaire that assesses the patients' perception of their COPD and measures the impact of COPD on their life. The CRQ-SAS refers to the CRQ-Self-administered format and contains 20 standardised dyspnea questions. The first part of the questionnaire contains 5 standardized activities and the patients must indicate how much shortness of breath they have experienced while performing each of the activities.

- Patients will also complete the CRQ-SAI questionnaire which contains a dyspnea domain
  that is individualized to each patient. Dyspnea items may be selected from a list of 26
  suggested items or may be written in by the patients. The patients are asked to select the 5
  activities associated with breathlessness that they perform frequently and are most important
  to them.
- Details of the CRQ-SAS are provided in Appendix 10.9.
- Details of the CRQ-SAI are provided in Appendix 10.10.

FD 0 ( 01177

Manier Dyspnea Indices [R96-2117]	
	The BDI performed at
visit 0 will be performed to determine eligibility.	

BI Trial No.: 1237.28

c03207491-01 Trial Protocol Page 53 of 137

Proprietary confidential information © 2016 Boehringer Ingelheim International GmbH or one or more of its affiliated companies Details of the Mahler Dyspnea Indices are provided in Appendix 10.12.

#### 5.3 ASSESSMENT OF SAFETY

#### Physical examination 5.3.1

Physical examinations are conducted at visit 1, at the end of each treatment period and at visit 10 in case of any findings at the end of treatment visit. The physical exam includes vital signs (blood pressure and pulse rate), height and weight.

BI Trial No.: 1237.28

c03207491-01 Trial Protocol Page 54 of 137

Proprietary confidential information © 2016 Boehringer Ingelheim International GmbH or one or more of its affiliated companies

#### 5.3.2 Vital Signs

Measurements of heart rate and blood pressure will be obtained immediately prior to forced spirometry measurement (FEV1 and FVC), with the patient seated and rested for a minimum of 5 minutes.

### 5.3.3 Safety laboratory parameters

Safety laboratory testing will be conducted (non-fasting) on all patients at the screening visit (visit 1), and at visits 6 and 9 (or at the withdrawal visit if the patient does not complete all study visits). Follow-up clinical laboratory testing will be performed at visit 10 if there are any clinically significant findings at visit 9. The laboratory tests at visit 1 will be considered as the baseline measurements. Laboratory specimens will be collected in the morning prior to the exercise testing. Patients should be instructed not to do any unaccustomed physical exercise 36 hours prior to laboratory testing.

Haematology, blood chemistry and ß-HCG will be analysed by the local laboratory of each participating site or, where appropriate, locally selected central laboratory. Laboratory data will be collected but not captured in the eCRF or transferred to the sponsor. It is the responsibility of the investigator to evaluate changes in laboratory values and reporting of adverse event should be followed according to the definitions outlined in section 5.3.6.1.

#### Haematology

Haemoglobin, haematocrit, red blood cell count, white blood cell count including differential (neutrophils, lymphocytes, monocytes, eosinophils, basophils), total eosinophil count and platelet count.

#### Blood chemistry

Alkaline phosphatase, Lactate Dehydrogenase (LDH), Gamma-Glutamyl Transpeptidase (Gamma-GT), Serum glutamic-oxaloacetic transaminase (SGOT), Serum glutamic-pyruvic transaminase (SGPT), glucose, calcium, inorganic phosphorus, uric acid, urea nitrogen, creatinine, total protein, potassium, sodium, chloride, total bilirubin, creatinine phosphokinase.

## **Pregnancy Testing**

A serum human chorionic gonadotropin (HCG) test will be done at visit 1 in all females of childbearing potential. Urine pregnancy testing will be performed at visit 4, 6, 7, 9, and 10 in females of childbearing potential.

BI Trial No.: 1237.28

c03207491-01 Trial Protocol Page 55 of 137

Proprietary confidential information © 2016 Boehringer Ingelheim International GmbH or one or more of its affiliated companies

## 5.3.4 Electrocardiogram

A standard 12-lead ECG at rest will be performed on all patients at visits 1, 6 and 9. An ECG will be repeated at visit 10 in case of any findings at visit 9.

The purpose of the screening ECG (visit 1) is to obtain information about the patient's baseline conditions that may have not been elicited in obtaining the baseline conditions. Therefore, any significant findings from the examination are recorded on the Baseline Condition page. ECG will be completed using site's own equipment and ECG data will not be collected or captured in the eCRF. It is the responsibility of the investigator to evaluate the ECG and reporting of adverse events should be followed using the definitions outlined in section 5.3.6.1. In case of indication of a disease listed under the exclusion criteria, the patient should not be randomised for treatment.

## 5.3.5 Other safety parameters

- Heart rate, blood pressure in conjunction with spirometry
- Heart rate, SpO2, blood pressure in conjunction with exercise testing

#### 5.3.6 Assessment of adverse events

#### 5.3.6.1 Definitions of AEs

#### Adverse event

An adverse event (AE) is defined as any untoward medical occurrence in a patient or clinical investigation patient administered a pharmaceutical product and which does not necessarily have to have a causal relationship with this treatment.

An AE can therefore be any unfavourable and unintended sign (including an abnormal laboratory finding), symptom, or disease temporally associated with the use of a medicinal product, whether or not considered related to the medicinal product.

## **Adverse reaction**

An adverse reaction is defined as a response to ta medicinal product which is noxious and unintended. Response in this context means that a causal relationship between a medicinal product and an adverse event is at least a reasonable possibility. Adverse reactions may arise from use of the product within or outside the terms of the marketing authorisation or from occupational exposure. Conditions of use outside the marketing authorization include off-label use, overdose, misuse, abuse and medication errors.

BI Trial No.: 1237.28

c03207491-01 Trial Protocol Page 56 of 137

Proprietary confidential information © 2016 Boehringer Ingelheim International GmbH or one or more of its affiliated companies

### Serious adverse event

A SAE is defined as any AE which:

- results in death,
- is life-threatening,
- requires inpatient hospitalisation or prolongation of existing hospitalisation,
- results in persistent or significant disability or incapacity,
- is a congenital anomaly/birth defect, or
- is to be deemed serious for any other reason if it is an important medical event when based upon appropriate medical judgment which may jeopardize the patient and may require medical or surgical intervention to prevent one of the other outcomes listed in the above definitions.

Medical and scientific judgment should be exercised in deciding whether other situations should be considered serious reactions, such as important medical events that might not be immediately life threatening or result in death or hospitalisation but might jeopardise the patient or might require intervention to prevent one of the other outcomes listed above. Examples of such events are intensive treatment in an emergency room or at home for allergic bronchospasm, blood dyscrasias or convulsions that do not result in hospitalisation or development of dependency or abuse. Any suspected transmission via a medicinal product of an infectious agent is also considered a serious adverse reaction.

## AEs considered "Always Serious"

Cancers of new histology and exacerbations of existing cancer must be reported as a serious event regardless of the duration between discontinuation of the drug and the occurrence of the cancer.

In accordance with the European Medicines Agency initiative on Important Medical Events, Boehringer Ingelheim has set up a list of AEs, which by their nature, can always be considered to be "serious" even though they may not have met the criteria of an SAE as given above.

The latest list of "Always Serious AEs" can be found in the RDC. These events should always be reported as SAEs.

#### Adverse events of special interest (AESIs)

No AESIs have been defined for this trial.

#### **Intensity of AEs**

The intensity of the AE should be judged based on the following:

Mild: Awareness of sign(s) or symptom(s) that is/are easily tolerated

BI Trial No.: 1237.28

c03207491-01 Trial Protocol Page 57 of 137

Proprietary confidential information © 2016 Boehringer Ingelheim International GmbH or one or more of its affiliated companies

Moderate: Enough discomfort to cause interference with usual activity

Severe: Incapacitating or causing inability to work or to perform usual activities

## **Causal relationship of AEs**

The definition of an adverse reaction implies at least a reasonable possibility of a causal relationship between a suspected medicinal product and an adverse event. An adverse reaction, in contrast to an adverse event, is characterised by the fact that a causal relationship between a medicinal product and an occurrence is suspected.

Medical judgment should be used to determine the relationship, considering all relevant factors, including pattern of reaction, temporal relationship, de-challenge or re-challenge, confounding factors such as concomitant medication, concomitant diseases and relevant history.

Yes: There is a reasonable causal relationship between the investigational product administered and the AE.

No: There is no reasonable causal relationship between the investigational product administered and the AE.

BI Trial No.: 1237.28

c03207491-01 Trial Protocol Page 58 of 137

Proprietary confidential information © 2016 Boehringer Ingelheim International GmbH or one or more of its affiliated companies

Arguments that may suggest that there is a reasonable possibility of a causal relationship could be:

- The event is consistent with the known pharmacology of the drug
- The event is known to be caused by or attributed to the drug class
- A plausible time to onset of the event relative to the time of drug exposure
- Evidence that the event is reproducible when the drug is re-introduced
- No medically sound alternative etiologies that could explain the event (e.g. pre existing or concomitant disease, or co-medications)
- The event is typically drug-related and infrequent in the general population not exposed to drugs (Stevens-Johnson Syndrome)

Arguments that may suggest that there is no reasonable possibility of a causal relationship could be:

- No plausible time to onset of the event relative to the time of drug exposure is evident (e.g. pre-treament cases, diagnosis of cancer or chronic disease within days/weeks of drug administration; an allergic reaction weeks after discontinuation of the drug concerned)
- Continuation of the event despite the withdrawal of the medication taking into account the pharmacological properties of the compound (e.g. after 5 half-lives). Of note, this criterion may not be applicable to events whose time course is prolonged despite removing the original trigger
- Additional arguments amongst those stated before, like alternative explanation (e.g. situations where other drugs or underlying disease appear to provide a more likely explanation for the observed event than the drug concernted)
- Disapperance of the event event though the study drug treatment continues or remains unchanged

## 5.3.7 Adverse event collection and reporting

## **AE** Collection

[figure not shown]
The Investigator shall maintain and keep detailed records of all AEs in their patient files.

The following must be collected and documented on the appropriate eCRF by the investigator:

- From signing the informed consent onwards through the Residual Effect period (REP), until individual patient's end of trial:
  - All AEs (serious and non-serious).
- After the individual patient's end of trial:
  - The Investigator does not need to actively monitor the patient for AEs but should only report relevant SAEs of which the Investigator may become aware of.

c03207491-01 Trial Protocol Page 59 of 137

Proprietary confidential information © 2016 Boehringer Ingelheim International GmbH or one or more of its affiliated companies

The REP is defined as 21 days after the last trial medication application. All AEs which occurred through the treatment phase and throughout the REP will be considered as on treatment please see section 7.3.3. Events which occurred after the REP will be considered as post treatment events.

## AE reporting to sponsor and timelines

The investigator must report SAEs and non-serious AEs which are relevant for the reported SAE on the BI SAE form via fax immediately (within 24 hours ) to the Sponsor's unique entry point (country specific contact details will be provided in the ISF). The same timeline applies if follow-up information becomes available. In specific occasions the investigator could inform the Sponsor upfront via telephone. This does not replace the requirement to complete and fax the BI SAE form.

#### **Information required**

For each AE, the investigator should provide the information requested on the appropriate eCRF pages and the BI SAE form. The Investigator should determine the causal relationship to the trial medication and any possible interactions between the investigational drugs and a Non-Investigational Medicinal Product (NIMP)/Auxiliary Medicinal Product (AMP).

The following should also be recorded as an SAE in the eCRF and SAE form (if applicable):

- Worsening of the underlying disease or of other pre-existing conditions.
- Changes in vital signs, ECG, physical examination and laboratory test results, if they are judged clinically relevant by the Investigator.

If such abnormalities already pre-exist prior trial inclusion they will be considered as baseline conditions.

BI Trial No.: 1237.28

c03207491-01 Trial Protocol Page 60 of 137

Proprietary confidential information © 2016 Boehringer Ingelheim International GmbH or one or more of its affiliated companies

All (S)AEs, including those persisting after individual patient's end of trialmust be followed up until they have resolved, have been sufficiently characterized, or no further information can be obtained.

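### Protocol 5.3.7 has sites record disease worsening and clinically relevant test changes as SAEs without any seriousness test, contradicting the SAE definition in 5.3.6.1

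*Protocol*

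**What the plan says.** The definition is in Protocol 5.3.6.1. Under Serious adverse event it opens "A SAE is defined as any AE which" and lists six criteria: death, threat to life, hospitalisation or its prolongation, lasting or significant disability, congenital anomaly, and important medical event. It also treats suspected transmission of an infectious agent through a medicinal product as serious. Under Always Serious it adds new or worsening cancers and a sponsor list kept in the data-capture system, and says "These events should always be reported as SAEs".

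Protocol 5.3.7, under Information required, then says: "The following should also be recorded as an SAE in the eCRF and SAE form (if applicable". Two items follow. The first is "Worsening of the underlying disease or of other pre-existing conditions". The second covers changes in vital signs, ECG, physical examination and laboratory results that the investigator judges clinically relevant.

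The sentence just before reads "For each AE, the investigator should provide the information requested on the appropriate eCRF pages and the BI SAE form". The subsection before that, on reporting timelines, sets a 24-hour limit and is narrower: "The investigator must report SAEs and non-serious AEs which are relevant for the reported SAE on the BI SAE form via fax immediately".

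**The concern.** Neither item in 5.3.7 refers to the seriousness criteria. An exacerbation managed at home, or a clinically relevant but non-serious laboratory change, would be an SAE under 5.3.7 and an ordinary AE under 5.3.6.1. Sites have no stated rule for which section governs.

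Seriousness coding has these consequences in the plan:

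- It starts the 24-hour report to the sponsor (Protocol 5.3.7).
- It places the patient in the SAE table (SAP 7.8.1).
- It removes the event from the other-significant AE table, which SAP 7.8.1 limits to non-serious events. A non-serious COPD worsening that led to discontinuation would move from that table to the SAE table.
- After a patient's end of trial, the investigator need report only relevant SAEs (Protocol 5.3.7, AE Collection).
- For a patient randomised twice, SAEs and exposure are the only safety data reported (SAP 6.2).

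In the last two cases, seriousness decides whether an event is reported at all.

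The situation is foreseeable. Protocol 4.2.1 allows several treatments for acute exacerbations during the treatment period. Protocol 3.3.4.1 counts steroid courses separately from hospital admissions, so the protocol expects COPD worsening that need not meet the hospitalisation criterion.

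**Working it through.** The check is mainly a comparison of text.

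**Step 1. What each place requires.**

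| Place | Event | Condition for SAE status |
|---|---|---|
| Protocol 5.3.6.1 | Any AE | One of six criteria, infectious-agent transmission, or the Always Serious rules |
| Protocol 5.3.7, first item | Disease worsening | None stated |
| Protocol 5.3.7, second item | Vital signs, ECG, examination, laboratory changes | Clinical relevance only |
| Protocol 5.3.3 | Laboratory findings | "reporting of adverse event should be followed according to the definitions outlined in section 5.3.6.1" |
| Protocol 5.3.4 | ECG findings | "reporting of adverse events should be followed using the definitions outlined in section 5.3.6.1" |
| SAP 7.8.2 and 7.8.4 | Clinically significant laboratory and ECG findings | Handled as baseline conditions or adverse events; not serious by default |

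The AE definition in 5.3.6.1 also names an abnormal laboratory finding as something that can be an AE. For laboratory and ECG changes, 5.3.7 is therefore the outlier. For disease worsening, vital signs and physical examination there is no such cross-reference, but the general definition in 5.3.6.1 still applies and 5.3.7 still conflicts with it.

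**Step 2. Does the qualifier in parentheses resolve it?** It stands after the reference to the SAE form, is undefined, and cites no criterion. At most it limits when the form is used. The instruction to record the event as an SAE in the eCRF remains.

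**Step 3. Could the Always Serious list resolve it?** The list is not in the documents, so whether any particular event is on it cannot be checked. It could not cover every clinically relevant test change without contradicting Protocol 5.3.3 and 5.3.4 and SAP 7.8.2 and 7.8.4.

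**Step 4. The preceding sentence.** Read literally, it asks for SAE-form information for every AE. The timelines subsection requires the form only for SAEs and for non-serious AEs relevant to a reported SAE. The Pregnancy subsection of 5.3.7 shows that the condition can be stated plainly: there the SAE form is used only if an SAE accompanies the pregnancy.

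**Step 5. Size per patient.** Inputs:

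- 102 patients planned on each treatment (Protocol synopsis).
- AE analyses count patients, not events (SAP 7.8.1).
- Percentages are given to one decimal place (SAP 7).

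One patient wrongly counted as having an SAE adds 1/102 = 0.0098, or 0.98 percentage points, shown as 1.0. The plan states no figure to reproduce. No total can be computed, because the documents give no rate of COPD worsening, no SAE rate, and nothing on how sites would read the sentence.

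**The case against.** The strongest reply is that this is a drafting slip for AE or (S)AE and that experienced sites will see through it. The (S)AE form appears later in the same subsection, AE collection covers serious and non-serious events alike, and 5.3.3, 5.3.4 and the SAP all point to the intended rule for laboratory and ECG findings. The qualifier can also be read as: enter the event in the eCRF, and use the SAE form where the timelines subsection requires it. A slip is plausible, but that is an inference about intent. The sentence is still an instruction to sites, and the charitable reading leaves the words requiring SAE status in the eCRF.

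The fault in the preceding sentence is milder. It can be read as describing what information to supply, with the timelines subsection deciding when the form is due. That is arguable, but the literal conflict remains.

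Several points about consequence stand:

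- A discontinuation event stays visible in the table of AEs leading to treatment discontinuation, whatever its seriousness code (SAP 7.8.1).
- The 0.98-point figure converts one patient to a percentage and does not estimate the effect. The safety denominator is the treated set, so 102 is only the planned count. A patient who already has a genuine SAE on that treatment adds nothing.
- The error runs towards over-reporting and does not hide serious events.
- A site's coding habit applies to the same patients on both treatments in this double-blind crossover, so it does not in itself favour either.
- Safety analyses are descriptive, with no hypothesis testing (Protocol 7.3.3).

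These points limit the importance of the conflict but do not remove it.

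**Conclusion.** The inconsistency is real. Protocol 5.3.7 gives SAE status to disease worsening and to clinically relevant test changes without a seriousness test, against 5.3.6.1, 5.3.3, 5.3.4 and SAP 7.8.2 and 7.8.4. The stakes are unnecessary expedited reports and an SAE table whose content depends on which section a site followed. Laboratory and ECG data do not enter the eCRF (Protocol 5.3.3 and 5.3.4), so the sponsor's database holds no such values against which to check a site's classification.

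The total effect is unknown. The per-patient figure in the working assumes the planned 102 per treatment and a patient with no other SAE on that treatment. The primary analysis, the sample size and the comparison of efficacy are untouched. The textual conflict is certain; how sites would act on it is not. It should be corrected, but it does not threaten the trial's main conclusion.

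**What to change.** Reconcile 5.3.7 with 5.3.6.1 by changing two sentences under Information required.

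1. Replace the sentence that introduces the two items with, for example: *Record each of these as an AE in the eCRF. Classify it as an SAE, and complete the SAE form, only where section 5.3.6.1 makes it serious, including its rules on infectious-agent transmission, cancers and the Always Serious list.*
2. Replace the sentence before it with, for example: *Complete the relevant eCRF pages for every AE. Complete the BI SAE form only for SAEs and for non-serious AEs that bear on a reported SAE.*

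If the sponsor does intend these items to be serious in every case, the protocol should say so in 5.3.6.1 and bring 5.3.3, 5.3.4 and SAP 7.8.2 and 7.8.4 into line.

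The cost of the two-sentence correction is the protocol change and a note to sites. It needs no new data, visits or analyses.
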